#### **5.2.8. Graphical Displays**

For SALT and ALODEX, the LS mean percent change and 95% CI will be plotted over time by treatment group. For the binary efficacy endpoint of proportion of subjects achieving  $\geq 50\%$  hair regrowth relative to baseline based on the SALT and ALODEX scores, the percentage and 95% CI will be plotted over time by treatment group.

#### **5.2.9. Open-Label Extension**

For the open label extension period, efficacy will be evaluated based on the SALT, ALODEX, Scalp-ClinRO, Scalp-PRO, and SGITS. Descriptive summary statistics will be reported for the following:

- SALT score and change from baseline
- ALODEX Score and change from baseline
- Number (%) of subjects for each category of the Scalp-ClinRO (target patch and entire scalp)
- Number (%) of subjects for each category of the Scalp-PRO (target patch and entire scalp)
- Number (%) of subjects for each category of SGITS.

Summaries will include changes from baseline (study day 1) and changes from the end of the DB study (Visit 10). All by visit summaries will utilize the normal study visit based on CRF collection.

The efficacy summaries will be presented for the following subject groups based on the DB treatment assignments and the duration since end of DB period:

- Subjects who were randomized to Vehicle in the double-blind portion of the study
- Subjects who were randomized to ATI-50002 12% in the double-blind portion of the study who also entered the OLE less than 7 days from the end of their DB treatment period
- Subjects who were randomized to ATI-50002 12% in the double-blind portion of the study who also entered the OLE more than 7 days, but less than 60 days from the end of their DB treatment period
- Subjects who were randomized to ATI-50002 12% in the double-blind portion of the study who also entered the OLE at least 60 days from the end of their DB treatment period
- Subjects who were randomized to ATI-50002 46% in the double-blind portion of the study who also entered the OLE less than 7 days from the end of their DB treatment period

- Subjects who were randomized to ATI-50002 46% in the double-blind portion of the study who also entered the OLE more than 7 days, but less than 60 days from the end of their DB treatment period
- Subjects who were randomized to ATI-50002 46% in the double-blind portion of the study who also entered the OLE at least 60 days from the end of their DB treatment period.

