5.5. Open-Label Extension

At Week 24 (Visit 10) or Week 28 (Visit 11), the subject may be given the option to move into the OLE treatment if the subject meets the OLE entry criteria in Section 5.5.1.

- If the subject declines the OLE, Visit 11 (Post-treatment) will be the last double-blind study visit.
- If the subject chooses to continue into the OLE, she/he must sign an OLE ICF/Accent, complete Visit 10 or Visit 11, as appropriate, and OLE Visit 1, prior to being dispensed open-label drug and receiving continued study medication application instructions. The subject will be scheduled for OLE Visit 2.
- If the subject enrolls in open-label treatment within 30 days of completion of Week 24 (Visit 10) or Week 28 (Visit 11), OLE Visit 1 will be conducted to obtain consent/assent and perform the procedures in the Schedule of Assessments. This will be considered the official date that the subject initiated OLE treatment.
- If the subject enrolls in open-label treatment > 30 days after completion of Week 28, OLE Visit 1 will be conducted in order to obtain consent/ assent, and complete the procedures detailed in the Scheduled of Events. This will be considered the official date that the subject initiated OLE treatment and the scheduling of subsequent visits will be based on this date.

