#### **Open-Label Extension (OLE):**

In the OLE, safety, tolerability and efficacy will be assessed. All subjects enrolled in the OLE will apply ATI-50002 Topical Solution, 0.46% to the entire scalp or patchy areas with a ½” margin, twice daily for 24 weeks (6 months). In addition, subjects with eyebrow loss may apply study

medication to the entire eyebrow(s) twice daily for 24 weeks. Subjects will be followed for safety, tolerability and efficacy as detailed in Section 1.2 Schedule of Assessments. Subjects who entered the OLE and for administrative reasons had a gap of > 30 days between completion of Visit 10 or Visit 11 and entry into the open-label should return for the OLE Visit 1 and have the procedures detailed in the Schedule of Assessments.

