- If the subject enrolls in open-label treatment > 30 days after completion of Week 28, OLE Visit 1 will be conducted to obtain consent/ assent, and complete the procedures detailed in the Scheduled of Events. This will be considered the official date that the subject initiated OLE treatment and the scheduling of subsequent visits will be based on this date.

 SALT, ALODEX and Photography is performed at OLE Visit 1 (if Week 28 is < 30 days) only if there is a significant change from the last double-blind study visit.

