#### Day 1 (OLE)

Day 1(OLE) is defined as the date of the Visit 10 assessment for all subjects entering the OLE period.

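### The SAP starts the open-label extension at Visit 10 for everyone, so after a treatment gap Period Day is too large and the change from Visit 10 mixes off-drug with on-drug change

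*SAP*

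**What the plan says.** **Start of the OLE.** The SAP's definition (3.3.6) reads: "Day 1(OLE) is defined as the date of the Visit 10 assessment for all subjects entering the OLE period". Period Day is counted from the Day 1 of each period. Protocol 5.5 says of OLE Visit 1: "This will be considered the official date that the subject initiated OLE treatment". The SAP repeats this in footnote 14 to its schedule (1.2). For entry more than 30 days after Week 28 the footnote says: "This will be considered the official date that the subject initiated OLE treatment and the scheduling of subsequent visits will be based on this date".

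**Delayed entry.** Subjects may enter at Visit 10, at Visit 11 or later. SAP 1.1 provides for subjects who "had a gap of > 30 days between completion of Visit 10 or Visit 11 and entry into the open-label", and neither document sets an upper limit.

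**Reference values.** SAP 5.2.9 plans two: "Summaries will include changes from baseline (study day 1) and changes from the end of the DB study (Visit 10". It plans no change from a value taken at OLE entry.

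**Groups.** OLE efficacy is shown in groups "based on the DB treatment assignments and the duration since end of DB period". Each active arm is split into under 7 days, "more than 7 days, but less than 60 days from the end of their DB treatment period", and those "who also entered the OLE at least 60 days from the end of their DB treatment period". Vehicle subjects form one group.

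**Scores available.** SALT and ALODEX are scheduled at Visit 11, and at OLE Visit 1 when Visit 11 was more than 30 days before. In the 30-days-or-less column they are repeated only if the investigator sees a significant change (footnote 15).

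**The concern.** The SAP contains two OLE start dates. One agrees with the protocol; the one that drives Period Day does not, although SAP section 6 reports no departure from the protocol's analyses.

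The reference value is the second issue. A subject who stops double-blind treatment at Visit 10 and starts open-label drug weeks later has an untreated interval in between. Subtracting Visit 10 combines that interval with the response to open-label drug. For active-arm subjects it may contain loss of regrown hair. For vehicle subjects it is the natural course of a disease that Protocol 2.1 describes as waxing and waning, and they are the only group receiving drug for the first time. Long-term efficacy is a stated objective (Protocol 4.4; SAP 2), so a reader of the OLE tables will want to know what happened on open-label drug.

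**Working it through.** **Plan's own design figure.** The power statement (Protocol 11.1, SAP 3.1) reproduces: 24 / (38 × √(2/40)) = 2.82; 2.82 − 1.96 = 0.86; normal power 0.806 (0.797 with the t distribution), against the stated 80%. Nothing below depends on it.

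**Inputs.** Visit 10 is Day 169 and Visit 11 is Day 197, each ± 3 days. OLE Week 4 is OLE treatment day 29 and OLE Week 24 is day 169 (schedules in Protocol 6.3 and SAP 1.2). Let g be the days from Visit 10 to OLE Visit 1.

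**Size of g.**
- Entry at Visit 11: 197 − 169 = 28 days; with both windows, 28 − 6 = 22 to 28 + 6 = 34.
- Entry more than 30 days after a nominal Week 28: more than 28 + 30 = 58 days.

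**Effect on Period Day and on the interval measured.** Under the SAP, Period Day = OLE treatment day + g. The untreated share of the interval from Visit 10 is g / (g + 28) at OLE Week 4 and g / (g + 168) at OLE Week 24. The gaps of 60 and 90 days are illustrative.

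| g (days) | Period Day at OLE Week 24 (169 if counted from OLE Visit 1) | Untreated share to OLE Week 4 | Untreated share to OLE Week 24 |
|---|---|---|---|
| 28 | 169 + 28 = 197 | 28/56 = 50% | 28/196 = 14% |
| 60 | 169 + 60 = 229 | 60/88 = 68% | 60/228 = 26% |
| 90 | 169 + 90 = 259 | 90/118 = 76% | 90/258 = 35% |

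These are shares of time, not of hair.

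**Effect on the change score.** Change from Visit 10 = (change from Visit 10 to OLE Visit 1) + (change from OLE Visit 1). A higher SALT score is worse, so off-drug loss enters with a plus sign. Assume an on-drug change of −20 SALT points and a gap loss of 5, 10 or 20 points. The change from Visit 10 is then −15, −10 or 0, while the change from OLE Visit 1 stays at −20. All these point values are assumptions.

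**Strata.** Under 7, over 7 but under 60, and 60 or more leave exactly 7 days unassigned. The middle stratum runs from 8 to 59 days and the last has no upper limit, so untreated time still varies within both.

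**The case against.** Much can be said for the plan as written.

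- **Day 1(OLE) reaches little.** It feeds only Period Day. OLE efficacy is summarised by nominal visit (SAP 3.3.7, 5.2.9), and OLE treatment-emergent events count from the start of OLE medication (SAP 3.3.6). A reader might infer that the wrong start date distorts the efficacy or adverse-event tables; the documents do not support that.
- **The strata help.** They keep delayed active-arm subjects apart from those who entered within days, for whom Visit 10 is a fair reference. Mixing remains in the longer-gap strata, but it is labelled.
- **The protocol's long-term endpoint is served.** Change from study Day 1 is reported. Change from Visit 10 also answers a fair question: whether the double-blind response was held or recovered.
- **A later score is not guaranteed.** A subject entering soon after Visit 10 may have neither a Visit 11 score nor a repeat at OLE Visit 1. Scalp-ClinRO and Scalp-PRO are scheduled at neither visit, so Visit 10 remains their last scheduled value before the OLE.
- **A floating reference has a cost.** Which visit supplies it depends on the gap and, within 30 days, on whether a change was noticed.

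These points stand. They limit the consequences and argue for adding a summary rather than replacing one. They do not resolve the two start dates, supply an on-drug change for subjects with a gap, or place the subject with a 7-day gap.

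**Conclusion.** The definition of Day 1(OLE) contradicts the protocol and the SAP's own footnote. Period Day is too large by exactly the gap: nominally 28 days (22 to 34) for entry at Visit 11, and more than 58 days for entry over 30 days after Week 28. In subjects with a gap, the change from Visit 10 cannot be read as response to open-label drug. One gap length is left out of the active-arm groups, and the vehicle group hides its gaps.

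Two stronger readings should be resisted. A reader might infer that off-drug loss inflates the open-label effect. The sign is the opposite: loss before OLE dosing makes the change from Visit 10 look worse and understates OLE response. A reader might also take the 24 points in the power statement as an expected regrowth and shrink it by some relapse rate. That figure is a detectable between-arm difference in percent change, and the documents give no off-drug loss, so its size cannot be stated.

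OLE efficacy is descriptive and untested. The change from study Day 1, the OLE adverse-event rule and the primary analysis are unaffected. This is a definition to correct and a summary to add, not a threat to the trial's main result.

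**What to change.** 1. In SAP 3.3.6, define Day 1(OLE) as the date of first OLE application (OLE Visit 1), in line with Protocol 5.5.
2. In SAP 5.2.9, add SALT and ALODEX change from the last non-missing value on or before that date, whether from Visit 10, Visit 11 or OLE Visit 1. For a same-day score, require that it precedes the first application. This extends the SAP's existing baseline rule to the OLE. Report how many subjects contribute each reference visit, and keep the Visit 10 change as a second summary.
3. Take the reference from all recorded scores. The double-blind visit windows (SAP Table 1) end at Day 182, so a Visit 11 score has no window there.
4. Make the first active-arm gap group 7 days or less.
5. Describe the distribution of the gap in the vehicle group.

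The cost is a few SAP definitions and one added summary for each of two scores. No new assessments are needed. Where no later score was taken, Visit 10 remains the reference.

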### **5.3. SAFETY**

All safety analyses will be performed on the Safety Population. Values for all safety variables will be listed by subject and visit (as applicable).

#### **5.3.1. Adverse Events**

Adverse events will be mapped to a preferred term and system organ classification by Medical Dictionary for Regulatory Activities (MedDRA) version 22.0.

An overall summary will be presented which includes the number of TEAEs and the number and percentage of subjects who experienced at least one TEAE. This summary will also include:

- Any TEAE
- Any Serious TEAE
- Any Mild TEAEs
- Any Moderate TEAEs
- Any Severe TEAEs
- Any Related TEAEs
- Any TEAEs leading to discontinuation
- Any Related TEAEs leading to discontinuation

Additional summaries of TEAEs will be provided showing the number and percentage of subjects who experienced at least one TEAE. These summaries will be presented by system organ class (SOC), preferred term (PT) and maximum severity. If a participant reports the same PT multiple times within the same SOC, that PT will only be counted once within that SOC for that participant. As with the PT, if a participant reports multiple conditions within the same SOC, that SOC will only be counted once for that participant. In the summary, SOC will be listed in ascending alphabetical order; PTs will be listed in order of descending frequency for all participants within each SOC.

The occurrence of TEAEs related to study medication (possibly/probably) will be tabulated by SOC, PT and maximum severity. Serious adverse events (SAE) will be presented by system organ class (SOC), preferred term (PT) and maximum severity. SAE related to study medication will also be presented by SOC and PT.

All AEs reported will be listed by individual subject, showing both verbatim and preferred terms. All AEs reported with a start date prior to the initiation of study medication will be excluded from the TEAE tables but will be included in the listings.

Missing onset dates will be imputed as previously outlined in Section 3.3.5 as required to determine TEAEs.

### **5.3.2. Clinical Laboratory Assessments, Vital Signs, and Physical Examination Findings**

Descriptive summaries of quantitative clinical laboratory results (hematology, chemistry, and urinalysis) and their change from baseline values will be presented by study visit and treatment group. Observed values of categorical urinalysis data will be displayed with frequencies and percentages. All laboratory data will be listed for individual subjects.

Treatment-emergent abnormal laboratory assessments will be based on the lab provided normal ranges. If the baseline laboratory assessment is normal and shifts to Low or High post-baseline, then the laboratory value is considered a TE abnormal laboratory value. For each protocol specified lab test, the number and percent of subjects reporting a TE abnormal lab will be reported.

All laboratory summaries will be limited to the tests specified in the protocol.

Descriptive summaries of vital signs and their change from baseline will be presented by study visit and treatment group and all vital signs will be listed.

Post-baseline PE findings will be listed.

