9.2.4. Study Medication Interruption and Discontinuation Criteria

9.2.4.1 Study Medication Interruption

Treatment with ATI-50002 Topical Solution should be temporarily interrupted in the event of severe adverse events considered related to ATI-50002, or in the event of one or more of the abnormal laboratory values in Table 2.

Table 2: Study Medication Interruption Criteria

Laboratory Test	Hold Study Medication if:	Resume Study Medication if:
WBC count	$< 2 \times 10^9/L$	$\geq 2.5 \times 10^9/L$
ANC	$< 1 \times 10^9/L$	$\geq 1.5 \times 10^9/L$
Lymphocyte count	$< 0.5 \times 10^9/L$	$\geq 0.75 \times 10^9/L$
Platelet count	$< 75 \times 10^9/L$	$\geq 100 \times 10^9/L$
Hemoglobin	$< 8 \text{ g/dL}$ or a decrease $> 2\text{ g/dL}$	$\geq 10 \text{ g/dL}$
AST or ALT	$> 3 \times \text{ULN}$	$< 2 \times \text{ULN}$ or within 20% of Baseline values
Serum creatinine	$> 2 \times \text{ULN}$	$< 1.5 \times \text{ULN}$ or within 10% of Baseline value

If a subject has one or more of the abnormal laboratory values noted in Table 2, the investigator or designee upon receipt and review of the central laboratory report should instruct the subject to hold study medication applications. The investigator or designee should ask the subject about symptoms, concomitant illnesses and medications and repeat the test(s) as soon as possible. The Medical Monitor must be notified of dose interruptions due to SAEs considered related to study medication or laboratory abnormalities noted in Table 2.

If the retest confirms the abnormal laboratory value, then the study medication should continue to be held followed by repeat testing once a week or sooner at the discretion of the investigator. The subject should be followed until the laboratory abnormality(s) return to normal or to baseline values.

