#### Adverse Event (AE)

An AE is any untoward medical occurrence in a subject administered a study medication(s) and which does not necessarily have a causal relationship with the study medication. An AE can therefore be any unfavorable and unintended sign or symptom associated with the use of a study medication (including an abnormal laboratory finding), whether related to the study medication. Thus, any new, clinically significant worsening of an existing sign, symptom or disease, should be considered an AE. Every new episode or clinically significant worsening of a chronic condition (*e.g.*, headaches, seasonal allergies, depression, or hypertension) should be reported as a separate AE, even if the condition is reported in the subject's medical history.

Treatment-Emergent Adverse Event (TEAE)

For the interim analysis of the DB treatment period, any recorded AE that occurs on or after the initiation of study medication and within 31 days after the date of Visit 10 or after the date of last DB dose of study medication will be considered treatment-emergent. For the OLE period analysis, an AE that occurs on or after the initiation of OLE study medication and within 31 days after the date of last dose of study medication will be considered treatment-emergent.

Treatment-emergent Laboratory Abnormalities

A treatment-emergent laboratory abnormality is defined as a result in which the baseline value is within normal laboratory limits and the post-baseline value is outside normal laboratory limits. If the relevant baseline assessment is missing, then any post-baseline value outside normal laboratory limits is treatment-emergent.

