#### Section 14.3 Safety

- 78. Table 14.3.1.1 Overall Summary of Adverse Events, Safety Population
- 79. Table 14.3.1.2 Treatment-Emergent Adverse Events by System Organ Classification, Preferred Term, and Greatest Severity, Safety Population
- 80. Table 14.3.1.3 Treatment-Emergent Adverse Events by System Organ Classification and Preferred Term, Safety Population
- 81. Table 14.3.1.4 Treatment-Emergent Serious Adverse Events by SOC and PT, Safety Population
- 82. Table 14.3.1.5 Treatment-Emergent Adverse Events Related to Study Drug by SOC and PT, Safety Population

83. Table 14.3.1.6 Treatment-Emergent Adverse Events Leading to Discontinuation of Study Drug by SOC and PT, Safety Population
84. Table 14.3.1.7 Study Drug Related Treatment-Emergent Adverse Events Leading to Discontinuation of Study Drug by SOC and PT, Safety Population
85. Table 14.3.4.1.1 Summary of Hematology Results and Change from Baseline by Visit, Safety Population
86. Table 14.3.4.1.2 Summary of Treatment-Emergent Abnormal Hematology by Visit Safety Population
87. Table 14.3.4.2.1 Summary of Serum Chemistry Results and Change from Baseline by Visit, Safety Population
88. Table 14.3.4.2.2 Summary of Treatment-Emergent Abnormal Serum Chemistry by Visit, Safety Population
89. Table 14.3.4.3.1 Summary of Urinalysis Results and Change from Baseline by Visit, Safety Population
90. Table 14.3.4.3.2 Summary of Treatment-Emergent Abnormal Urinalysis by Visit, Safety Population
91. Table 14.3.5.1.1 Summary of ECG Results and Change from Baseline by Visit, Safety Population
92. Table 14.3.5.1.2 Proportion of Subjects with Abnormal ECG Interpretations by Visit, Safety Population
93. Table 14.3.5.2.1 Summary of Vital Signs and Change from Baseline, Safety Population

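### The treatment-emergent laboratory count merges shifts to Low with shifts to High, which dilutes a one-directional signal, mainly in hematology

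*SAP*

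**What the plan says.** - **Definition.** SAP 3.3.6 (Treatment-emergent Laboratory Abnormalities) defines the event as one where "the baseline value is within normal laboratory limits and the post-baseline value is outside normal laboratory limits". If baseline is missing, any out-of-range later value counts.
- **Rule and report.** SAP 5.3.2 repeats the rule for a normal baseline that "shifts to Low or High post-baseline, then the laboratory value is considered a TE abnormal laboratory value". For each test named in the protocol, "the number and percent of subjects reporting a TE abnormal lab will be reported".
- **Tables.** SAP 8.1 lists "Summary of Treatment-Emergent Abnormal Hematology by Visit" (Table 14.3.4.1.2) and "Summary of Treatment-Emergent Abnormal Serum Chemistry by Visit, Safety Population" (Table 14.3.4.2.2), with a urinalysis counterpart (Table 14.3.4.3.2). The titles add a visit dimension but no direction. No shift table and no table of Protocol Table 2 thresholds is listed. SAP 5.3.4 and 8.2 carry the same design into the open-label extension.
- **What the protocol acts on.** Protocol 9.2.4.1 interrupts treatment "in the event of one or more of the abnormal laboratory values in Table 2". That table concerns low WBC, ANC, lymphocytes, platelets and hemoglobin, and high AST/ALT and creatinine. The discontinuation criteria in 9.2.4.2 point the same way for these tests.

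**The concern.** The count treats a fall in neutrophils below range and a rise above range as the same event. The laboratory risks that the protocol names are directional, and safety is part of the primary objective. A reader comparing arms on this table cannot tell which direction produced a difference. Shifts in the direction of no concern enter numerator and comparison alike, so a real increase in low counts looks smaller than it is.

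The other planned outputs do not supply the missing figure. Change-from-baseline summaries do not count subjects who cross a limit, minimum and maximum show one subject each, and listings give no rate by arm. Protocol 11.5 calls for clinically significant abnormal results to be tabulated by treatment group, but SAP 8.1 lists no table for that.

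**Working it through.** The documents state no laboratory rate, so there is no figure to reproduce. The arm size of 40 is from SAP 3.1. **All rates below are assumptions** chosen to show how the count behaves.

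**1. Formulas.** Let L and H be the proportions shifting to Low and to High, with subscripts A (active) and V (vehicle). SAP 3.3.7 uses one result per analysis window in the summaries, so at a given visit a subject can shift in only one direction and the merged proportion is L + H.

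- Merged difference = (L_A − L_V) + (H_A − H_V)
- Merged ratio = (L_A + H_A) / (L_V + H_V)

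If H_A = H_V, the difference is unchanged and the ratio moves towards 1. If Low is raised on active, the merged difference is zero only when H_V − H_A = L_A − L_V, that is, when High is rarer on active by exactly the amount that Low is commoner.

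**2. Equal opposite shifts in both arms.** Low 15% vs 2.5% (6 vs 1 of 40), High 10% in both arms (4 vs 4).

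- Low alone: ratio 15/2.5 = 6.0; difference 15 − 2.5 = 12.5 points.
- Merged: 25% vs 12.5% (10 vs 5 of 40); ratio 25/12.5 = 2.0; difference 12.5 points.

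The separate ratio of 6.0 rests on one vehicle subject. With Low at 20% vs 5% instead (ratio 4.0), an equal High background of 0, 2.5, 5, 10 or 15% gives merged ratios of 4.0, 3.0, 2.5, 2.0 and 1.75. The difference is 15 points throughout.

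**3. Fewer opposite shifts on active.** Vehicle has 2 Low and 6 High.

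- Active 8 Low and 2 High: Low 20% vs 5%; merged 10 vs 8 subjects (25% vs 20%), so 15 points become 5.
- Active 8 Low and 0 High: merged 8 vs 8 (20% vs 20%), difference 0. This is complete masking.

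**4. Can treatment itself cause step 3?** Take a normally distributed analyte with a 95% reference range, so vehicle has 2.5% in each tail, and move the active arm down by s SD. Then L_A = Φ(−1.96 + s) and H_A = Φ(−1.96 − s). This ignores the normal-baseline condition.

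| s (SD) | Low, active | High, active | Merged, active (vehicle 5.0%) | Ratio, Low | Ratio, merged |
|---|---|---|---|---|---|
| 0.25 | 4.4% | 1.4% | 5.7% | 1.75 | 1.14 |
| 0.5 | 7.2% | 0.7% | 7.9% | 2.89 | 1.58 |
| 0.75 | 11.3% | 0.3% | 11.7% | 4.53 | 2.33 |
| 1.0 | 16.9% | 0.2% | 17.0% | 6.74 | 3.40 |

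Merged values are computed before rounding. A drug that lowers a count also removes some shifts to High, so part of the rise is offset. In every row the merged ratio stays above 1: a plain downward shift weakens the signal but does not erase it.

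**The case against.** **The SAP never says that Low and High will share a row.** Its table list is headed as proposed, gives titles only, and no shells are available. A table with two rows per test would comply. This stands as a limit on certainty: the merged count is the plain reading, not an explicit instruction. But nothing in the text requires a split.

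**Direction survives elsewhere.** This also stands. Values and changes are summarized by visit and arm (SAP 5.3.2), with minimum and maximum (SAP 5). All laboratory results are listed, and there is a separate listing of abnormalities. Protocol 8.4.3 requires clinically significant out-of-range results after first treatment to be recorded as AEs, which are tabulated by arm. That AE count is, however, filtered by investigator judgement. Categorical urinalysis results get frequencies of their own, so the merged tables are not the only categorical laboratory output.

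**Table 2 thresholds are not normal limits.** Correct: examples are ANC below 1 × 10⁹/L and AST/ALT above 3 × ULN. Splitting the count would not show how many subjects reach them. Table 2 matters here only because it shows which direction is of concern for each test.

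**Exact cancellation is contrived.** Largely right. It needs a specific imbalance in opposite shifts, and no figure in the documents supports one. With equal background the absolute difference is untouched.

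**No decision depends on the count.** Laboratory output is descriptive, with no planned test or threshold. This limits the consequence but does not make the merged display informative.

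**Conclusion.** The point holds as a reporting gap that should be closed. As written, the plan gives no by-arm count, by direction, of subjects crossing a normal limit in hematology or chemistry, beyond results that investigators judge clinically significant and report as AEs.

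The expected effect is dilution: under the assumed rates, a ratio of 6.0 is displayed as 2.0, with the difference still 12.5 points. The size depends on how common opposite shifts are; with none, nothing changes. The conclusion rests on reading SAP 5.3.2 as one count per test (per visit in the table titles).

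A reader might infer three stronger claims, none of which the documents support:

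- **That a safety signal would be hidden outright.** This needs fewer opposite shifts on active than on vehicle, by enough to offset the rise.
- **That high liver enzymes would be masked in the same way as low counts.** That depends on how often enzymes shift to Low. Neither that rate nor the laboratory's lower limits are given, so the concern is mainly for hematology.
- **That directional information is lost from the trial.** It remains in the change summaries, extremes, listings and AEs.

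**What to change.** Add one sentence to SAP 5.3.2: for each quantitative test, normal-to-Low and normal-to-High are reported as separate rows, each with n and percent by treatment group. Apply it to the treatment-emergent hematology, chemistry and quantitative urinalysis tables in SAP 8.1 and to their open-label counterparts in SAP 8.2. In any row that spans visits, a subject with both shifts counts in both rows. Subjects with a missing baseline, whom SAP 3.3.6 already counts, go in the row for their post-baseline direction, with a footnote.

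The existing rule already needs each result classified as Low, normal or High, so no new data or derivation is required. The only downside is longer tables. The change is best made before the double-blind data are unblinded, so that the split is not chosen after seeing the results.
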